4 OBJECTIVES AND ENDPOINTS

Table 4-1:	Objectives and Endpoints	
Objectives		Endpoints
To monitor target eng combination with eith advanced solid tumor	gagement of BMS-986226 administered alone and in her nivolumab or ipilimumab in participants with 's	Summary measures of changes from baseline (% or absolute change) in cell surface ICOS expression on T cells and ICOS- ligand+ B cells

^a These endpoints will be assessed based on RECIST v1.1 or PCWG3 (prostate only) criteria and will be determined based on tumor measurements occurring every 8 weeks (± 1 week) during the treatment period and at least every 12 weeks (± 2 week) in the response and survival follow-up periods. For Part A, scans will be collected centrally and may be reviewed by BICR at a later date or at any time during the study. For Parts B, C, D and E, scans will be collected centrally to be reviewed in real time by BICR.

TIL = tumor-infiltrating lymphocytes.

Revised Protocol No.: 04 Date: 31-May-2019

5 STUDY DESIGN

Figure 5-1: Study Design Schematic

* Note: Arms B2 and C2 will enroll only if additional safety, PK, and PD data are required to inform dose expansion decisions. The dose levels assessed in B2 and C2 will not exceed those evaluated in Part A, B1, or C1.

5.1 Overall Design

This is a Phase 1/2, open-label study of BMS-986226 administered as a monotherapy or in combination with either nivolumab or ipilimumab in participants with advanced solid tumors. The study will be conducted in 3 parts: 1) dose-escalation monotherapy (Preliminary Safety Cohorts and Part A); 2) dose-escalation combination therapy with either nivolumab (Part B) or ipilimumab (Part C); 3) a dose expansion phase with either nivolumab (Part D) or ipilimumab (Part E).

Monotherapy consists of 2 different parts as follows:

- Preliminary Safety Cohorts with BMS-986226 administered as monotherapy at 2 mg and 8 mg once every 4 weeks (Q4W) for 24 weeks
- Part A, with BMS-986226 administered at 25 mg, 80 mg, 200 mg, 400 mg, and 800 mg Q4W for 24 weeks

Parts B and C consist of different combination cohorts comprising:

- B1: BMS-986226 administered every 12 weeks (Q12W) + nivolumab 480 mg Q4W at a starting dose level of BMS-986226 one dose level lower than a monotherapy dose (Part A) that has cleared the DLT period.
- B2: BMS-986226 Q4W + nivolumab 480 mg Q4W at a starting dose level of BMS-986226 tested in part B1.
- C1: BMS-986226 Q12W + ipilimumab 3 mg/kg Q4W at a starting dose level of BMS-986226 one dose level lower than a monotherapy dose (Part A) that has cleared the DLT period.
- C2: BMS-986226 Q4W + ipilimumab 3 mg/kg Q4W at a starting dose level of BMS-986226 tested in Part C1.

Parts B1 and C1 will enroll concurrently. Parts B2 and C2 will enroll if preliminary data from Part A or Parts B1 and C1 suggest a more frequent dose regimen than Q12W and if additional safety, PK, or PD data are required to optimize dose and/or schedule selection (see Section 5.1.2.2 [Parts B1 and B2] and Section 5.1.2.3 [Parts C1 and C2]). Parts B1/C1 and B2/C2 can enroll concurrently and participants will be alternately assigned to all open cohorts.

The doses of BMS-986226 for Parts B and C (combination with nivolumab or ipilimumab) will be determined using all available safety (clinical and laboratory), PK, and target engagement/PD data, as well as modeling recommendations within the Bayesian hierarchical modeling framework, ie, the BLRM-Copula model, by incorporating single-agent toxicity profiles of both BMS-986226 (Preliminary Safety Cohorts and Part A) and nivolumab or ipilimumab¹⁸ and any available combination toxicity data from Parts B and C (for subsequent doses of BMS-986226 in Parts B and C), PK/PD modeling, and will not exceed the maximum administered dose (MAD) of BMS-986226 monotherapy in the Preliminary Safety Cohorts and Part A (see Section 5.1.2.1).

At no point will the dose of BMS-986226 administered in combination with nivolumab or ipilimumab (Parts B and C) exceed the dose of BMS-986226 that has been demonstrated previously to be safe in the monotherapy dose-escalation arm (Part A), nor at any point during

combination therapy in Parts B and C will the BMS-986226 dose exceed the highest dose determined to be tolerated in the monotherapy dose-escalation arm (Part A). In addition, the starting dose level of BMS-986226 used in combination with nivolumab or ipilimumab (Parts B and C) will be one dose level lower than a monotherapy (Part A) dose that has cleared the DLT period.

Parts B and C will consist of combination dose escalation cohorts aimed to explore the kinetics of ICOS-receptor downmodulation and re-expression (and/or change in selected target engagement/PD () following administration of BMS-986226 in the presence of multiple doses of nivolumab Q4W (Part B) or ipilimumab (Q4W) (Part C). Up to 3 different doses of BMS-986226 will be administered in each of Parts B1 and C1 and an additional 6-12 participants will be enrolled in up to 3 different dose cohorts in Parts B2 and C2:

• Doses that induce or are predicted to induce different levels of ICOS receptor downmodulation, including at least one dose that induces near-complete receptor downmodulation (and/or change in selected target engagement/PD (and/or)) for a duration of at least 4 weeks. These dose levels will allow characterization of the ICOS receptor re-expression kinetics after near-complete downmodulation for a period of time equal to, less than, and/or exceeding the dosing intervals used in Part A. Understanding ICOS receptor kinetics will help inform testing BMS-986226 dosing intervals in future study(ies). Subsequent doses will also be evaluated by BLRM-Copula for toxicity.

Dose levels will be determined based on all available safety (clinical and laboratory) and PK data, as well as changes in peripheral target engagement markers (eg, ICOS down regulation on T cells and ICOS + B cells) from previous and completed portions of current cohorts and/or the BLRM/BLRM-Copula model whenever applicable.

Study Part	Study Treatment	Cohorts
Preliminary Safety	BMS-986226	• CC
Cohorts and Part A	monotherapy	• CRC
		• HNSCC
		• MEL
		• NSCLC
		• PRC
		• RCC
		• TNBC
		• UCC
		Other Advanced Epithelial Solid Tumors
Parts B and C	BMS-986226 +	• CC
	nivolumab or ipilimumab	• CRC
		• HNSCC
		• MEL

Table 5.1-1:Study Cohorts per Part

		1
Study Part	Study Treatment	Cohorts
		NSCLC
		• PRC
		• RCC
		• TNBC
		• UCC
		Other Advanced Epithelial Solid Tumors
Parts D and E BMS-986226 + nivolumab or ipilimumab		• To be determined based on safety, tolerability, PK, and PD data from Parts A, B, and C

Table 5.1-1:	Study Cohorts per Part
--------------	-------------------------------

For Parts A, scans will be collected centrally and may be reviewed by BICR at a later date or at any time during the study. For Parts B, C, D and E scans will be collected centrally to be reviewed in real time by BICR.

Physical examinations, vital sign measurements, 12-lead electrocardiogram (ECG), and clinical laboratory evaluations will be performed at selected times throughout the dosing interval. Participants will be closely monitored for AEs throughout the study. Blood will be collected at 30, 60, and 100-day follow-up visits (Section 9.5) after study treatment administration for PK analysis.

Participants will complete up to 4 phases of the study: screening, treatment, safety follow-up, and response/survival follow-up, as described below. Total duration of participation in the study is approximately 4 years.

The study design schematic is presented in Figure 5-1.

5.1.1 Screening

The screening phase will last for up to 28 days and take place prior to the first administration of study treatment. During the screening phase, the participant's initial eligibility will be established, and written informed consent will be obtained. Tumor biopsies will be collected for all participants and sent for central evaluation of ICOS expression by immunohistochemistry, and all participants will receive the tetanus booster vaccine 3-7 days prior to Cycle 1 Day 1 of first administration of study treatment. Stool will be collected for microbiota composition analysis. Participants will be enrolled using the Interactive Response Technology (IRT). The screening assessments are shown in Table 2-1.

5.1.2 Treatment Phase

The treatment phase in the Preliminary Safety Cohort and Part A consists of up to six 4-week treatment cycles (1 cycle = 28 days). In the Preliminary Safety Cohort and Part A, each treatment cycle will consist of BMS-986226 monotherapy for a total of 24 weeks.

Dose levels for Parts B and C will be determined based on all available safety (clinical and laboratory) and PK data, as well as changes in peripheral target engagement markers (eg, ICOS

downregulation on T cells and ICOS + B cells) from previous and completed portion of current cohorts, and will be guided by the BLRM/BLRM-Copula model whenever applicable.

In Parts B1 and C1, 4 week cycles will be used, such that BMS986226 + nivolumab or ipilimumab will be administered starting on Cycle 1 Day 1. Nivolumab and ipilimumab will be administered on Day 1 of each cycle. BMS-986226 will be administered Q12W, or on Day 1 of every third cycle (Cycle 1 Day1, Cycle 4, Day1, Cycle 7 Day1, etc.). Participants on Parts B1 and C1 may continue treatment for up to a total of 2 years.

The treatment phase in Parts B2 and C2 will consist of BMS-986226 + nivolumab or ipilimumab administered on Day 1 of each cycle and will be enrolled if additional safety, PK, or PD data is required to optimize dose and/or schedule selection. In parts B2 and C2 BMS-986226 will be administered Q4W and participants may continue treatment for a total of 2 years.

Following each treatment cycle, the decision to treat a participant with additional cycles of study treatment will be based on tumor assessment evaluations performed every 8 weeks $(Q8W \pm 1 \text{ week})$ and completed before the first dose in the next cycle. Tumor progression or response endpoints will be assessed using Response Evaluation Criteria In Solid Tumors (RECIST) v1.1 (Appendix 5) or PCWG3, for prostate only (Appendix 11).

Treatment beyond progression with additional cycles of study treatment may be allowed for up to a maximum of 24 weeks for Part A and 2 years for Parts B, C, D, and E in select participants with initial RECIST v1.1 or PCWG3 (prostate only) defined progressive disease after discussion and agreement between the Principal Investigator and the BMS Medical Monitor/Study Director (or designee) that the benefit/risk assessment favors continued administration of the study treatment (eg, participants are continuing to experience clinical benefit as assessed by the investigator, tolerating treatment, and meeting other criteria specified in Section 8.1.2).

Participants with a response of unconfirmed progressive disease, SD, PR, or CR at the end of a given cycle will continue to the next treatment cycle. Participants will generally be allowed to continue study treatment until the first occurrence of 1) completion of the maximum number of cycles, 2) confirmed progressive disease, 3) clinical deterioration suggesting that no further benefit from treatment is likely, 4) intolerability to therapy, or 5) a participant meeting criteria for discontinuation of study treatment as outlined in Section 8.1. Individual participants with confirmed CR will be given the option to discontinue study treatment on a case-by-case basis after specific consultation and agreement between the investigator and BMS Medical Monitor/Study Director (or designee) in settings where benefit/risk justify discontinuation of study treatment.

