5.1.2.4 Combination Expansion Arms (Parts D and E)

The purpose of the cohort expansion is to gather additional safety, tolerability, preliminary efficacy, PK, and PD information regarding BMS-986226 in combination with either nivolumab (Part D) or ipilimumab (Part E). Continuous evaluation of toxicity events in the cohort expansions will be performed throughout enrollment in the expansion cohorts. All participants treated with BMS-986226 in combination with either nivolumab or ipilimumab are recommended to receive premedications, as described in Section 7.1, in order to reduce the risk of infusion-related reactions. If, at any time, the aggregate rate of treatment-related toxicities meeting DLT criteria exceeds 33% across all participants treated the findings will be discussed and further enrollment will be interrupted. Depending on the nature and grade of the toxicity, and after assessing the risk/benefit ratio, a new dose for all cohorts may be initiated at a lower dose level.

The dose and schedule of BMS-986226 in Parts D and E will be determined based on all available safety, tolerability, efficacy, PK, and PD data from Parts A, B, and C. Parts D and E will be implemented following the revised protocol to define dose, schedule, and population.

Approximately 40 participants will be enrolled in each of Parts D and E. Safety, efficacy, PK, and PD data will be used to determine the precise patient population that will be enrolled in the expansion arms.

Participants with a response of unconfirmed progressive disease, stable disease, partial response, or complete response, at the end of a given cycle will continue to the next treatment cycle. Participants will be allowed to continue study treatment until the first occurrence of any of the following:

- Completion of the maximum number of cycles
- Confirmed progressive disease
- Clinical deterioration suggesting that no further benefit from treatment is likely
- Intolerability to therapy
- Participant meets the criteria for discontinuation of study treatment as shown in Section 8.2.

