5.1.5 Treatment Beyond Progression

Treatment beyond progression may be allowed in select participants with initial RECIST v1.1 or PCWG3 (prostate only) defined progressive disease after discussion and agreement with the BMS Medical Monitor/Study Director (or designee) that the benefit/risk assessment favors continued administration of study treatment (eg, participants are continuing to experience clinical benefit as assessed by the investigator, tolerating treatment, and meeting other criteria specified in (Section 8.1.2).

Participants must be re-consented with an informed consent form (ICF) addendum to continue treatment beyond progression. Treatment beyond progression will require continued tumor assessments.

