8 DISCONTINUATION CRITERIA

8.1 Discontinuation from Study Treatment

Participants **must** discontinue IP (and non-IP at the discretion of the investigator) for any of the following reasons:

- Participant's request to stop study treatment
- Any clinical AE, laboratory abnormality, or intercurrent illness that, in the opinion of the investigator, indicates that continued participation in the study is not in the best interest of the participant
- Termination of the study by BMS
- Loss of ability to freely provide consent through imprisonment or involuntary incarceration for treatment of either a psychiatric or physical (eg, infectious disease) illness. (Note: Under specific circumstances and only in countries where local regulations permit, a participant who has been imprisoned may be permitted to continue as a participant. Strict conditions apply and BMS approval is required.)
- Pregnancy
- Documented and confirmed disease progression as defined by RECIST v1.1 (see Appendix 5) or PCWG3 (prostate cancer only) (see Appendix 11) unless participant meets criteria for treatment beyond progression (Section 8.1.2)
- Clinical deterioration while receiving active study treatment that, in the opinion of the investigator, indicates that continued participation in the study is not in the best interest of the participant
- Discretion of the investigator
- Inability to comply with the protocol requirements
- Individual participants with confirmed CR will be given the option to discontinue study treatment on a case-by-case basis after specific consultation and agreement between the investigator and BMS Medical Monitor/Study Director (or designee) in settings where benefit/risk justifies discontinuation of study treatment
- Any Grade 4 drug-related AE or laboratory abnormality (including, but not limited to, creatinine, AST, ALT, or total bilirubin), except for the following events that do not require discontinuation:

- Grade 4 neutropenia \leq 7 days
- Grade 4 lymphopenia, leukopenia, or asymptomatic amylase or lipase abnormalities
- Isolated Grade 4 electrolyte imbalances/abnormalities that are not associated with clinical sequelae and are corrected with supplementation/appropriate management within 72 hours of their onset

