8.1.2 Treatment Beyond Disease Progression

As described in Section 5.4.3, accumulating evidence indicates that a minority of participants with solid tumors treated with immunotherapy may derive clinical benefit despite initial evidence of progressive disease. Participants will be permitted to continue on study treatment beyond initial

RECIST v1.1 defined progressive disease (see Appendix 5) or PCWG3 (prostate cancer only) (see Appendix 11) as long as they meet the following criteria:

- Investigator-assessed clinical benefit and no rapid disease progression
- Continue to meet all other study protocol eligibility criteria
- Tolerance of study treatment
- Stable performance status
- Treatment beyond progression will not delay an imminent intervention to prevent serious complications of disease progression (eg, CNS metastases)
- Participant provides written informed consent prior to receiving any additional BMS-986226, nivolumab, or ipilimumab treatment using an ICF describing any reasonably foreseeable risks or discomforts, or other alternative treatment options

The assessment of clinical benefit should take into account whether the participant is clinically deteriorating and unlikely to receive further benefit from continued treatment. If the investigator feels that the participant continues to achieve clinical benefit by continuing treatment with the study treatment, the participant should remain on the study and continue to receive monitoring according to the Schedule of Activities (see Section 2). All decisions to continue treatment beyond initial progression must be discussed with the BMS Medical Monitor/Study Director (or designee), and an assessment of the risk/benefit of continuing with study treatment must be documented in the study records. Participants will be re-consented to explain the rationale for this ongoing treatment.

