8.1.3 Discontinuation Due to Further Progression (Confirmed Progression)

Participants will continue to receive monitoring according to the on-treatment assessments in Section 2. Radiographic assessment by CT (preferred) or MRI (described in Section 9.1) is required when participants continue post-progression study treatment and should be performed at each scheduled tumor assessment 4 to 6 weeks following initial disease progression to determine whether there has been continued progressive disease or not. Participants should discontinue study treatment upon evidence of further progression, defined as an additional 10% or greater increase in tumor burden volume from the time of initial progression (including all target lesions and new measurable lesions).

The tumor burden volume from the time of initial progression should be used as the reference baseline for comparison with the post-progression assessment.

Any new lesion considered non-measurable at the time of initial progression may become measurable and therefore must be included in the tumor burden measurement as follows:

• For solid tumors: new lesions are considered measurable at the time of initial progression if the longest diameter is at least 10 mm (except for pathological lymph nodes, which must have a short axis of at least 15 mm).

For statistical analyses that include the investigator-assessed progression date, participants who continue treatment beyond initial investigator-assessed, RECIST v1.1 or PCWG3 (prostate cancer only) defined progression will be considered to have investigator-assessed progressive disease at the time of the initial progression event.

For participants who discontinue post-progression study treatment, no additional radiographic assessments will be required.

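### The sentences that keep participants with unconfirmed progression on treatment (5.1.2, 5.1.2.4) are not tied to the conditions and re-consent in 5.1.5 and 8.1.2, and the 4–6 week scan in 8.1.3 is not on the 8-week schedule

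*Combined protocol and SAP*

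**What the plan says.** **After a first progression.** Section 5.1.2 says: "Participants with a response of unconfirmed progressive disease, SD, PR, or CR at the end of a given cycle will continue to the next treatment". The paragraph just before it says that treatment past initial progression may be allowed in selected participants, with investigator and sponsor agreement on benefit and risk, and cites the criteria in 8.1.2. Section 5.1.2.4, on Parts D and E, says: "Participants with a response of unconfirmed progressive disease, stable disease, partial response, or complete response, at the end of a given cycle will continue". It carries no such paragraph and does not refer to 5.1.5 or 8.1.2.

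Section 5.1.5 again speaks of selected participants and adds: "Participants must be re-consented with an informed consent form (ICF) addendum to continue treatment beyond progression". Section 8.1.2 lists what must hold: investigator-assessed benefit without rapid progression, tolerance, stable performance status, continued eligibility, no delay to an urgent intervention, and written consent before any further dose. It sends every such decision to the Medical Monitor for discussion.

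**At confirmed progression.** Sections 5.1.2 and 5.1.2.4 list it as ending treatment. Section 8.1 lists "Documented and confirmed disease progression as defined by RECIST v1.1" (or PCWG3) as a mandatory reason to stop, but exempts participants who meet 8.1.2. Section 8.1.3 ends treatment on further progression, an additional increase of 10% or more in tumor burden.

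**Imaging after first progression.** Section 8.1.3 says imaging "should be performed at each scheduled tumor assessment 4 to 6 weeks following initial disease progression". Table 2-2 and Section 9.1.1 set on-treatment scans every 8 weeks (± 1 week), and Sections 7.3.1 and 7.3.4 anchor that schedule to the first dose.

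**The concern.** The same event, a first progression on treatment, is handled in two ways. One sentence groups it with stable disease and response and moves the participant to the next cycle. Other sections make the next dose depend on a benefit test, a discussion with the sponsor and a new consent. A coordinator working on an expansion arm would naturally turn to 5.1.2.4, which has only the first version. That section also refers to Section 8.2 for the criteria to stop treatment, but 8.2 covers leaving the study; the treatment criteria are in 8.1.

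What is at stake is mainly consent and the benefit test before dosing past progression, and then a consistent answer to who remains on treatment. The scan wording adds a practical difficulty. If the assessment that establishes further progression has to be both scheduled and 4 to 6 weeks later, the calendar does not provide it, and sites will settle the matter in different ways.

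**Working it through.** **1. The passages side by side**

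| Situation | 5.1.2 | 5.1.2.4 | 5.1.5 | 8.1 / 8.1.2 / 8.1.3 |
|---|---|---|---|---|
| First (unconfirmed) progression | Conditional in one paragraph, unconditional in the next | Unconditional | Selected participants, sponsor agreement, re-consent | 8.1.2: criteria, discussion and consent before further dosing |
| Confirmed or further progression | Treatment ends | Treatment ends | Silent | 8.1: treatment ends unless 8.1.2 is met. 8.1.3: treatment ends |

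Two things follow.

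- The progression item in 8.1 covers confirmed progression only. A participant with a first progression who fails the 8.1.2 criteria therefore meets no progression-based reason to stop in 8.1, only general ones such as investigator discretion or clinical deterioration.
- The exemption in 8.1 points to 8.1.2, which is written for initial progression. It cannot readily serve as an exemption from stopping at confirmed progression.

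**2. The scan calendar**

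Inputs: a cycle is 28 days (5.1.2); scans precede dosing at Cycles 3, 5 and 7 (9.1.1); the window is ± 7 days (Table 2-2, 9.1.1); the schedule runs from first dose (7.3.1, 7.3.4); the interval asked for in 8.1.3 is 4–6 weeks, or 28–42 days.

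The plan's own interval is reproduced first. Day 1 of Cycle k falls 28 × (k − 1) days after first dose:

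- Cycle 3: 28 × 2 = 56 days
- Cycle 5: 28 × 4 = 112 days
- Cycle 7: 28 × 6 = 168 days

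The nominal gap is 56 days, or 8 weeks, as stated.

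Let *a* and *b* be the days by which two consecutive scans depart from their nominal dates. The gap is 56 + *b* − *a*.

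| Reading of the window | Range of *a*, *b* | Gap | Day pairs within 28–42 days |
|---|---|---|---|
| Both windows fully used | −7 to +7 | 42–70 days (6–10 weeks) | 1 of 15 × 15 = 225 (0.4%) |
| Scans precede on-time dosing | −7 to 0 | 49–63 days (7–9 weeks) | 0 |
| Window counted from previous scan | 56 ± 7 | 49–63 days (7–9 weeks) | 0 |

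The single pair in the first row is *a* = +7, *b* = −7, giving 56 − 7 − 7 = 42 days exactly. The 0.4% is a share of calendar combinations, not a probability. On the nominal schedule the next scan comes 8 − 6 = 2 to 8 − 4 = 4 weeks later than 8.1.3 asks.

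No table in Section 2 lists a 4–6 week scan after progression. Section 9.1.1 allows scans at other times if the investigator is concerned about progression, but as an option.

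**3. What does not move**

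- Section 8.1.3 dates investigator-assessed progression at the initial event, and 9.1.3 closes best overall response at first documented progression. Investigator-assessed progression dates are therefore the same whether or not the participant continues.
- The DLT period is 28 days in the Preliminary Safety Cohorts and 35 days in Parts A, B and C. The first scheduled scan falls no earlier than day 56 − 7 = 49, after that period has closed.

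**The case against.** The best defence is that the protocol should be read as a whole. Section 5.1.2 gives the conditional rule first, names Parts B to E, and cites 8.1.2, so the later sentence can be taken as a summary. Both 5.1.2 and 5.1.2.4 stop treatment for clinical deterioration, and 5.1.2 says only that participants will generally be allowed to continue. Nothing waives re-consent. The heading of 8.1.3 and the definition in 9.1.1 equate confirmed with further progression, so on that topic only the exemption in 8.1 is loose. Parts D and E will not open before a further revision.

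Much of this stands. It means that 5.1.2 contains both rules rather than only the permissive one, and that a rapidly deteriorating participant is not left unprotected. It does not link the two paragraphs of 5.1.2, supply the missing condition in 5.1.2.4, or give 8.1.3 a scheduled scan.

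A reader might infer three stronger things, none of which the documents support.

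- *The primary safety endpoint is distorted across sites.* Stopping for progression is not an adverse event leading to discontinuation, continuation decisions pass through the sponsor's Medical Monitor, and no count of participants continuing past progression is given. Exposure may differ, but no size can be derived.
- *Waiting for the scheduled scan doubles the doses given before confirmation.* If progression is seen just before Cycle 3, the Cycle 3 and Cycle 4 visits both precede the next scheduled scan. A scan at 4 weeks, before Cycle 4 dosing, would follow one visit; a scan at 5 or 6 weeks already follows two. The difference is 0 to 1 visit, and in Parts B1 and C1 BMS-986226 is given only every third cycle.
- *The 4–6 week scan is impossible.* An unscheduled scan can supply it, and a first progression seen on an unscheduled scan may leave a scheduled one in the right window.

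**Conclusion.** The point holds as a matter of internal consistency. Section 5.1.2.4, and one sentence of 5.1.2, permit without condition what 5.1.5 and 8.1.2 permit only under criteria, Medical Monitor discussion and re-consent. The exemption in 8.1 does not fit the rule for confirmed progression used elsewhere. The imaging sentence in 8.1.3 asks for a scheduled assessment that the calendar nominally places 2 to 4 weeks later and reaches at 6 weeks only in the extreme case.

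The consequence is confined to who stays on treatment, whether consent precedes further dosing, and when further progression can be established. The planned total of about 234 participants is only a ceiling on the number affected. The scan conclusion assumes 28-day cycles, a schedule anchored to first dose, and a first progression detected at a scheduled scan.

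**What to change.** Reconcile the passages in an amendment:

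- Link the continuation sentences in 5.1.2 and 5.1.2.4 expressly with 5.1.5 and 8.1.2, so that all four state one rule.
- Use one consistent statement on confirmed progression in 5.1.2, 5.1.2.4, 8.1 and 8.1.3, including what the exemption in 8.1 refers to.
- Make the imaging time in 8.1.3 agree with the Section 2 tables and 9.1.1.
- Correct the cross-reference in 5.1.2.4 from 8.2 to 8.1.

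Which continuation rule and which scan timing apply is the sponsor's clinical decision; the request is only that the text give one answer. The cost is wording, with no added participants. The 5.1.2.4 changes can go into the revision already foreseen before Parts D and E open. The others also concern the earlier parts and need not wait for it.
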